### 6.2 DETAILS OF TRIAL PROCEDURES AT SELECTED VISITS

At each visit, assessments should be performed as indicated in the Flow Chart and as detailed in Section 5.

In the treatment period, all assessments should be performed before the trial medication is taken. Exceptions to this are post-dose vital signs and ECGs

. Once the trial medication is administered / once all visit assessments are complete that require a fasting status, trial participants may eat as normal

Vital signs measurements should always precede the ECG, and the ECG should always be measured before any blood samples are taken (refer to the Flow Chart and Sections 5.2.2 and 5.2.4).

In the event of force majeure or other disrupting circumstances the visit indicated in Section 6.1 may have to be performed at the trial participant's home, remotely (by phone) or as a combination of home and remote visit. At this visit, the following assessments can be performed at the trial participant's home or remotely:

- concomitant therapy
- IRT call
- dispense trial medication
- train trial participant / provide refresher training / dispense / review results (home BP and HR monitoring;
- all AEs / SAEs / AESIs
- compliance check

Trial medication will not be collected at the visit performed remotely. Instead, the medication should be collected when the trial participant next visits the site, or when a visit is performed at the trial participant's home (see below).

The following assessments can be performed at the trial participant's home:

- anthropometric measures
- vital signs
- physical examination
- resting 12-lead ECG (using a portable ECG machine)

• collect trial medication

If safety laboratory sampling via the central laboratory is not possible from the investigational site in the event of force majeure or other disrupting circumstances (and is instead performed at the trial participant's home), analyses can be performed at a local laboratory. The results of the safety laboratory tests must be transferred to the Investigator who must ensure a medical review and document any clinically relevant safety issues as AEs. For a list of "minimum required safety laboratory parameters" refer to Section 5.2.3 and Table 5.2.3: 2.

All deviations from the original schedule of assessments as defined in the Flow Chart will be documented and the implications considered for the analysis of the trial data.

### 6.2.1 Screening period (Visit 1a and 1b)

No trial procedures should be performed unless the trial participant has consented to take part in the trial. Once a trial participant has consented, he / she is considered to be enrolled in the trial and to have started screening. The trial participant should be recorded on the enrolment log and be registered in the IRT system as a screened trial participant. Trial participants who are not eligible to proceed to Visit 2 (i.e. they fail screening at either Visit 1a or 1b) should be registered as a screen failure in the IRT system and the eCRF and no further follow-up is required. Also refer to Section 3.3 for guidance regarding re-screening (and re-testing) during the screening period.

The screening period is defined as the period prior to randomisation and the first administration of trial medication. It consists of 2 visits (refer to Flow Chart), namely Visit 1a and Visit 1b; these visits should ideally be completed within a period of 4 weeks, (i.e. Day 1, Visit 2). There is no minimum duration for the screening period. A trial participant can proceed from one visit to the next within the screening period as soon as all results from the previous visit are available and if he / she remains eligible for the trial.

At Visit 1a demographic information will be collected. This includes the following:

- age on the day of informed consent (in years)
- sex (male / female in order to describe the trial participant's sex at birth)
- for female trial participants: of childbearing potential yes / no in order to characterise the trial participant population and as a basis for contraception requirements
- ethnicity and race in order to sufficiently characterise the trial participant population, to support possible subgroup analyses if needed, and to support the calculation of the kidney function via the CKD EPI formula which requires a trial participant to be classified as black or non-black (unless not acceptable according to local regulations)

#### Baseline Conditions and Medical History

Information with respect to medical history / baseline conditions will also be collected at Visit 1a (e.g. relevant chronic diseases, current observable conditions and other relevant conditions, based on Investigator judgement, which may not be observable on the day of the

examination [e.g. because the trial participant is receiving concomitant therapy to treat the condition]). This includes any new clinically relevant findings identified during the

### 6.2.2 Treatment period(s)

screening period.

If a trial participant is deemed eligible for the trial following Visits 1a and 1b, the trial participant will be randomised at Visit 2 (Day 1) by using the IRT system. All Visit 2 assessments (refer to the Flow Chart) should have been completed prior to administration of the first dose of trial medication; exceptions are the post-dose vital signs and ECGs Each trial participant can be randomised only once into the trial. The randomised treatment period starts with Visit 2 and ends when a trial participant reaches the EoT visit (refer to the Flow Chart). The last dose of BI 685509 will be administered in the evening of the day before the EoT visit.

Trial participants will be assessed regularly at scheduled visits as specified in the Flow Chart. During the dose titration phase of the treatment period (refer to Section 4.1.4), scheduled visits are more frequent. It is of particular importance that the time window for these visits is adhered to since the trial participant must have taken the preceding dose of BI 685509 for at least seven consecutive days before any up-titration occurs (refer to Sections 4.1.4, 4.1.4.1 and 4.1.4.2). Unscheduled visits may also be arranged where necessary; assessments completed during an unscheduled visit will depend on the circumstances under which the visit was planned, and should be based on Investigator judgement.

should also be reminded to bring **Example 1** and the electronic BP and HR monitoring device with them to each trial visit (refer to Sections 5.2.2.1 and 5.6.1). Refresher training should be provided as required.

At every dispensing visit in the trial (refer to Flow Chart), an IRT call should be made.

### 6.2.2.1 End of treatment / Early discontinuation visit

Patients who successfully complete the entire 8 week treatment period should have the assessments for the EoT visit performed as indicated in the Flow Chart. Such patients should be registered as completed in the IRT system. End of trial medication must also be recorded on the corresponding eCRF.

For patients who discontinue trial medication prematurely (for whatever reason), an ED visit (refer to the Flow Chart) should be completed instead of the planned treatment period visit (refer to Section 3.3.4.1). Ideally the ED visit should be performed within seven days of discontinuing the trial medication. The assessments performed at the ED visit should be in accordance with the Flow Chart, with the following exceptions:

- HVPG: not required
- •
- •
- biobanking sampling: not required

Patients who discontinue treatment early should be registered as discontinued in the IRT system. End of trial medication must also be recorded on the corresponding eCRF.

At the EoT and / or ED visit, patients should be reminded about restrictions (refer to Section 4.2.2) that still need to be observed up until the EoS visit (refer to Section 6.2.3). Home BP and HR monitoring should continue between the EoT / ED visit and the EoS visit.

### 6.2.3 Follow-up period and trial completion

An EoS visit should be scheduled 2 weeks after an EoT and / or ED visit (refer to the Flow Chart and Section 3.3.4.1); participation in the trial is over once this visit has been completed; completion must be recorded on the corresponding eCRF.

When an EoS visit is performed after an ED visit, the assessments performed at the EoS visit should be in accordance with the Flow Chart, with the following exceptions:

For an individual patient, trial completion is defined as completion of the EoS visit within the specified time window and who has not discontinued trial medication prematurely. Following an EoS visit, the patient will return to standard medical care.

#### 7. STATISTICAL METHODS AND DETERMINATION OF SAMPLE SIZE

In this trial, the primary endpoint is the percentage change in HVPG from baseline (measured in mmHg) after 8 weeks of treatment. The purpose of this trial is to demonstrate the shorttime clinical activity of BI 685509 on trial participants with CSPH in decompensated cirrhosis after the first decompensation event.

#### 7.1 **NULL AND ALTERNATIVE HYPOTHESES**

Statistical testing is not planned for this trial. All analyses will be descriptive in nature. The endpoints will be investigated. However, it is not planned to test a statistical hypothesis with regards to these variables in a confirmatory matter. Instead, they will be described and evaluated by descriptive statistical methods.

#### 7.2 PLANNED ANALYSES

#### 7.2.1 **General considerations**

The analyses will be performed based on the following analysis sets:

- Enrolled set (ES) this analysis set includes all trial participants having signed informed consent and who were eligible for inclusion into the trial. The ES will be used for analyses of trial participant disposition
- Randomised set (RS) this analysis set includes all enrolled trial participants that were randomised to the trial medication. The RS will be used for demographic and baseline disease characteristics presentation
- Treated set (TS) the treated set includes all trial participants who were randomised to the trial medication and were treated with at least one dose. The TS will be used for all safety analyses
- Full analysis set (FAS) this analysis set includes all enrolled or randomised trial participants who received at least one dose of trial medication and have a baseline measurement for the primary endpoint recorded. The FAS will be used for the efficacy analyses

Further analysis sets will be defined in the TSAP, if needed.

Efficacy analyses will be performed based on the planned treatment (i.e. the treatment assignment at randomisation). Safety analyses will be based on the actual treatment received at the enrolment/randomisation visit.

Unless otherwise stated, baseline is defined as the latest measurement before the first trial medication intake.

### Boehringer Ingelheim BI Trial No.: 1366-0055 c42374778-02 Clinical Trial Protocol

374778-02Clinical Trial ProtocolPage 78 of 98Proprietary confidential information © 2023 Boehringer Ingelheim International GmbH or one or more of its affiliated companies

#### 7.2.2 Handling of Intercurrent Events

The expected intercurrent events of interest in this trial are:

- use of the following restricted concomitant therapy:
  - o NO-sGC-cGMP pathway activating therapies like NO-donors (e.g. glyceryl trinitrate, isosorbide di- or mono-nitrate, molsidomine), PDE-5-inhibitors (e.g. sildenafil, tadalafil, and vardenafil), non-specific PDE inhibitors such as dipyridamole and theophylline, or sGC-stimulators (e.g. riociguat)
- new onset of / dose change in existing NSBB / carvedilolconcomitant therapy
- occurrence of a decompensation event
- Premature discontinuation of assigned trial medication

The strategies for handling intercurrent events in this trial are as follows:

Treatment Policy: This is the effect of randomizing trial participants to a treatment arm regardless of treatment actually being taken. All intercurrent events will be handled according to the treatment policy approach as defined in ICH E9(R1).

Each analysis will reference the strategy for handling intercurrent events that it will be estimating. The estimand for each main analysis in this protocol is the combination of the relevant detailed clinical objective from Section 2.1 and this strategy.

Handling of the intercurrent events that are not listed above will be decided by the review and will be documented in the TSAP.

Page 79 of 98

Proprietary confidential information © 2023 Boehringer Ingelheim International GmbH or one or more of its affiliated companies

#### 7.2.3 Primary objective analyses

The primary endpoint (refer to Section 2.1.2) will be analyzed using an ANCOVA model in the FAS without imputing the missing data.

The model is as follows:

Percentage change of HVPG from baseline at Week 8 = overall mean	1
+ HVPG baseline	

+ treatment + use of NSBBs or carvedilol

- + type of first decompensation event
- + random error

This model includes effects accounting for the following sources of variation: 'treatment', 'use of NSBBs or carvedilol' and 'type of first decompensation event' are a fixed classification effects, and 'HVPG at baseline' is a linear covariate. The random error is assumed to be normally distributed with mean 0 and unknown variance  $\sigma^2$ . The analysis will only be used for estimation of treatment effects without hypothesis testing. Trial participants will be analysed according to the stratum to which they belong (regardless of any mis-assignment to treatment based on identification of the wrong stratum), as such an error occurs before randomisation and is therefore consistent with regulatory guidance. Procedures to follow if the analysis fails to converge will be described in the TSAP.

7.2.3.1 Sensitivity Analyses

Sensitivity analyses may be performed and will be described in more detail in the TSAP, if applicable.

#### 7.2.3.2 Subgroup Analyses

Any subgroup analyses planned for this trial will be described in the TSAP, if applicable.

#### 7.2.4 Secondary objective analyses

Unless otherwise stated, only descriptive statistics will be presented for the secondary endpoints defined in Section 2.1.3. The percentage of trial participants who have experienced the events of interest for secondary endpoints will be presented.

#### 7.2.5 Further objective analyses

Only descriptive statistics will be presented for further endpoints (defined in Section 2.2.2).

#### 7.2.6 Safety analyses

Adverse events will be coded using the Medical Dictionary for Drug Regulatory Activities (MedDRA). Standard BI summary tables and listings will be produced. All adverse events

with an onset between start of treatment and end of the REP, a period of 7 days after the last dose of trial medication, will be assigned to the on-treatment period for evaluation.

Safety analyses will be done by "treatment at onset" principle. All treated trial participants will be included in the safety analysis. In general, safety analyses will be descriptive in nature and will be based on BI standards. No hypothesis testing is planned.

Statistical analysis and reporting of adverse events will concentrate on treatment-emergent adverse events, i.e. all adverse events occurring between start of treatment and end of the REP. Adverse events that start before first drug intake and deteriorate under treatment will also be considered as 'treatment-emergent'.

Frequency, severity, and causal relationship of adverse events will be tabulated by system organ class and preferred term after coding according to the current version of the Medical Dictionary for Drug Regulatory Activities (MedDRA) at database lock.

Laboratory data will be analysed both quantitatively as well as qualitatively. The latter will be done via comparison of laboratory data to their reference ranges. Values outside the reference range as well as values defined as clinically relevant will be summarised. Treatment groups will be compared descriptively with regard to distribution parameters as well as with regard to frequency and percentage of trial participants with abnormal values or clinically relevant abnormal values.

Vital signs, physical examinations, or other safety-relevant data observed at screening, baseline, during the course of the trial and at the end-of-trial evaluation will be assessed with regard to possible changes compared to findings before start of treatment.

### 7.2.8 Interim Analyses

No interim analysis is planned but a Data Monitoring Committee (DMC) will be in place with tasks as described in section 8.7. Full details will be specified in the DMC charter. The primary role of the DMC is the ongoing evaluation of safety.

# 7.3 HANDLING OF MISSING DATA

No imputation of missing data is planned for the remaining endpoints. If a trial participant misses a visit, the missing data will not be imputed.

#### 7.4 RANDOMISATION

BI will arrange for the randomisation and the packaging and labelling of trial medication. The trial will be performed as a double-blind design with respect to placebo and active BI 685509. Trial participants will be randomised in blocks to one of the two treatment groups in a 1:1 ratio. The randomisation will be stratified by use (or not) of NSBBs or carvedilol and type of first decompensation event (ascites or variceal haemorrhage) (refer to Section 3.1).

The randomisation list will be generated using a validated system, which involves a pseudorandom number generator so that the assigned treatment will be reproducible but at the same time non-predictable. The block size will be documented in the CTR. Access to the codes will be controlled and documented.

#### 7.5 DETERMINATION OF SAMPLE SIZE

It is planned to enrol 40 trial participants in total in this trial: 20 trial participants per treatment group (active vs. placebo).

It will be considered as a positive signal if a mean percentage reduction of HVPG from baseline after 8 weeks of treatment of at least 15% is observed. it was assumed that the mean percentage reduction of HVPG from baseline at week 8 would be: 0% and 20% for placebo and BI 685509, respectively(with a standard deviation of 25% in each group) based on previous studies [R21-1984, R21-1945]. With the sample size of 40 (20 trial participants per treatment group), the probability to observe a mean percentage reduction of HVPG  $\geq$  10% in BI 685509 is 89.3%. This probability would be only 26.5% in case that the mean percentage reduction of HVPG from baseline is 5%. Probabilities of achieving an assumed treatment effect within different scenarios are presented in Table 7.5: 1.

 Table 7.5: 1
 Scenarios of probabilities of achieving the assumed treatment effect

Scenarios	Assumption of mean percentage reduction in	Probability that the observed treatment
	HVPG from baseline to week 8 	effect is $\geq 10\%$
Positive	20%	89.3%
	15%	73.5%
Negative	5%	26.5%
	0%	10.3%

SD = 25%

N=20 per treatment group

The calculations were performed using R 4.1.2.

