#### 2. TRIAL OBJECTIVES AND ENDPOINTS

#### 2.1 MAIN OBJECTIVES, PRIMARY AND SECONDARY ENDPOINTS

#### 2.1.1 Main objectives

The trial will investigate the safety and tolerability of BI 685509 in patients with CSPH in decompensated cirrhosis due to non-cholestatic liver diseases on top of standard of care. The primary objective is to estimate the percentage change in HVPG from baseline measured after 8 weeks in comparison to placebo. The primary analysis will be made for treated patients with baseline HVPG measurements (Full Analysis Set, FAS) as if all trial participants took treatment for the duration of the trial.

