# **3.3.4** Discontinuation of trial participants from treatment or assessments

Trial participants may discontinue trial treatment or withdraw consent to trial participation as a whole ("withdrawal of consent") with very different implications; please see Sections 3.3.4.1 and 3.3.4.2.

However, if the trial participants agree, they should stay in the trial. Even if continued trial treatment is not possible, they should attend further trial visits to ensure their safety and to collect important trial data.

Measures to control the withdrawal rate include careful trial participant selection, appropriate explanation of the trial requirements and procedures prior to trial enrolment, as well as the explanation of the consequences of withdrawal.

The decision to discontinue trial treatment or withdraw consent to trial participation and the reason must be documented in the trial participant files and CRF. If applicable, consider the requirements for AE collection reporting (see Section 5.2.6.2).

Trial participants who discontinue after randomisation will not be replaced and may not be re-enrolled later. However, the Sponsor may decide to randomise more trial participants than originally planned, to account for a reduced sample size, if trial participants terminate early due to e.g. trial disruption (such as measures to control a global pandemic).

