4. CHANGES IN THE PLANNED ANALYSIS OF THE STUDY

The Avenciguat program in patients with clinically significant portal hypertension (CSPH) is decided to be discontinued in May 2024. No subject has finished the 8-week treatment duration, leading to no HVPG data at Week 8 collected. Therefore, planned analysis around HVPG data in the CTP, i.e.,

- percentage change in HVPG from baseline after 8 weeks of treatment,
- occurrence of a response, which is defined as > 10% reduction from baseline HVPG after 8 weeks of treatment,

will not be performed. Only listing will be prepared.

Consequently, the reporting of intercurrent event, which supports HVPG analysis, is no longer of interest. All subjects are decided to be early discontinued.

c43185880-01

Proprietary confidential information © 2024 Boehringer Ingelheim International GmbH or one or more of its affiliated companies.

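### Section 7.5 sets the positive-signal benchmark at an observed 15% HVPG reduction but reports probabilities only for 10%, and attributes to the BI 685509 arm a figure that belongs to the difference from placebo

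*Protocol*

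**What the plan says.** Protocol Section 7.5 plans 20 participants per group. It assumes mean HVPG reductions of 0% on placebo and 20% on BI 685509, with an SD of 25% in each group. Three statements matter.

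- The benchmark: the trial shows a "positive signal if a mean percentage reduction of HVPG from baseline after 8 weeks of treatment of at least 15% is observed". The sentence does not say whether this is the BI 685509 arm mean or the difference from placebo.
- The probability in the text, for an observed reduction of at least "10% in BI 685509 is 89.3"%. It is worded as a quantity of the active arm.
- Table 7.5: 1, whose last column is headed "Probability that the observed treatment" effect is at least 10%. It gives 89.3%, 73.5%, 26.5% and 10.3% for true reductions of 20%, 15%, 5% and 0%. The first two rows are labelled as positive scenarios and the last two as negative.

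Section 2.1.1 frames the aim as a comparison: "The primary objective is to estimate the percentage change in HVPG from baseline measured after 8 weeks in comparison to placebo". Section 7.1 states that no statistical testing is planned.

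**The concern.** The benchmark is a rule about an observed value. Its cut-off is 15%, while every reported probability uses a cut-off of 10%. No part of the protocol or SAP links the two or gives a probability for 15%. The 15% cannot be the planning assumption, because that is stated separately as 0% against 20%.

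Section 7.5 also mixes two quantities. The text speaks of the active arm, whereas the table column and the primary objective point to the difference from placebo. The two have different standard errors, so one probability cannot serve for both.

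Without a hypothesis test there is no power or type I error to fall back on. The benchmark and its probabilities are all that Section 7.5 offers in support of 20 per group. A reader who pairs the printed 89.3% with the stated 15% rule will overrate the chance of a positive result. The same reader will also misjudge the chance of a false signal when the drug has no effect.

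**Working it through.** **Inputs, all from Protocol Section 7.5:** SD 25% in each group, 20 per group, true reductions of 20%, 15%, 5% and 0% (placebo 0%), thresholds of 10% and 15%.

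**Formula:** P(observed ≥ c) = Φ((d − c)/SE), with d the true reduction and c the threshold.

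- Difference between arms: SE = 25 × √(2/20) = 7.906
- BI 685509 arm mean: SE = 25/√20 = 5.590

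**Step 1. Reproduce the printed figures (threshold 10%).**

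| True reduction | Printed | Difference, normal | Difference, t 38 df | Arm mean, normal | Arm mean, t 19 df |
|---|---|---|---|---|---|
| 20% | 89.3 | 89.7 | 89.3 | 96.3 | 95.5 |
| 15% | 73.5 | 73.6 | 73.5 | 81.4 | 80.9 |
| 5% | 26.5 | 26.4 | 26.5 | 18.6 | 19.1 |
| 0% | 10.3 | 10.3 | 10.7 | 3.7 | 4.5 |

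For the first row, the difference gives Φ(10/7.906) = Φ(1.265) = 89.7%, and the arm mean gives Φ(10/5.590) = Φ(1.789) = 96.3%. All four printed values fit the difference to within 0.4 points. None fits the arm mean. The table is therefore correct for the difference, and the reference to the BI 685509 arm in the text is what is wrong.

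A small side point: three printed rows match the t version and the last matches the normal version. The 20% and 0% rows lie symmetrically about 10% and should sum to 100%, but 89.3 + 10.3 = 99.6.

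**Step 2. Apply the rule as stated (threshold 15%, normal).**

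| True reduction | Difference | Arm mean |
|---|---|---|
| 20% | Φ(5/7.906) = 73.6 | Φ(5/5.590) = 81.4 |
| 15% | 50.0 | 50.0 |
| 5% | 10.3 | 3.7 |
| 0% | 2.9 | 0.4 |

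At the planning assumption the printed 89.3% exceeds the probability for the 15% rule by 89.3 − 73.6 = 15.7 points on the difference, or 89.3 − 81.4 = 7.9 points on the arm mean. With no true effect, the chance of a false signal on the difference is 10.3% at a threshold of 10% and 2.9% at 15%.

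**Step 3. Number that would keep 89.3% at 15% on the difference.** Φ⁻¹(0.893) = 1.2426, so n = 2 × (25 × 1.2426/5)² = 77.2, or 78 per arm.

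**Step 4. Sensitivity to evaluable numbers (illustration).** The figures above need a Week 8 HVPG from all 20 in each arm. For the early discontinuation visit, Section 6.2.2.1 has "HVPG: not required". Section 3.3.4 says "Trial participants who discontinue after randomisation will not be replaced and may not be re-enrolled later", although it lets the sponsor randomise more participants to make up for a reduced sample. Under Section 7.2.3 the endpoint "will be analyzed using an ANCOVA model in the FAS without imputing the missing data". The documents give no dropout rate, so 18 and 16 evaluable per arm are assumptions. At a true 20%, on the difference:

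| Evaluable per arm | SE | Threshold 15% | Threshold 10% |
|---|---|---|---|
| 20 | 7.906 | 73.6 | 89.7 |
| 18 | 8.333 | 72.6 | 88.5 |
| 16 | 8.839 | 71.4 | 87.1 |

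**The case against.** The best reply is that the table is right for what its header says, so this is inconsistent wording and not a miscalculation. That stands: the printed values reproduce, and a reader can derive the missing probabilities from the SD and group size. They are unreported, not unobtainable.

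The two thresholds may also belong to different quantities: 15% to the change within the active arm, 10% to the treatment effect. Alternatively, 15% may only mark which true scenarios count as positive. The first reading is possible, but it still leaves the 15% rule without a probability. The second does not sit with the sentence, which speaks of a reduction being observed.

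With placebo assumed at 0%, the expected arm mean and the expected difference coincide, so naming the arm could pass as loose phrasing. The sampling errors still differ, by enough to move 89.3% to about 96%.

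Two further points are fair. A true effect equal to its threshold is met half the time whatever the sample size, so the 50.0% row says nothing particular about this design. The evaluable-number effect is small, at most 73.6 − 71.4 = 2.2 points over the range shown for the 15% rule, and is secondary.

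Finally, no go/no-go decision or stopping rule elsewhere refers to the benchmark, and it will never be applied here. SAP Section 4 reports: "No subject has finished the 8-week treatment duration, leading to no HVPG data at Week 8 collected". This limits the consequence to the design justification but does not remove the inconsistency.

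**Conclusion.** The point holds. Section 7.5 reports no probability for the benchmark it states, and it attributes to the BI 685509 arm a probability that belongs to the difference from placebo. At the assumed 20% effect, the 15% rule would be met with probability 73.6% on the difference or 81.4% on the arm mean, against the 89.3% printed for a 10% rule.

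These figures rest on normal sampling with the stated SD, 20 evaluable participants per arm, and simple means without the covariate adjustment of the primary model. The documents do not show whether 10% or 15% was intended, so the sponsor has to settle that. No error rate and no reported result is affected. It should be corrected because it is the only quantitative support given for the sample size.

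**What to change.** State one threshold and one quantity in Section 7.5, and make the text and Table 7.5: 1 agree. Defining the signal on the placebo-corrected mean percentage reduction at Week 8 would match Section 2.1.1. The options are:

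- **15% on the difference:** report 73.6%, 50.0%, 10.3% and 2.9% for true reductions of 20%, 15%, 5% and 0%, and say that 40 participants are kept with about 74% at the assumed effect.
- **15% on the BI 685509 arm mean:** say so, and report 81.4%, 50.0%, 3.7% and 0.4%.
- **10% on the difference:** change the benchmark sentence to 10% and replace the reference to the BI 685509 arm with the difference from placebo. Compute all four rows by one method: 89.7%, 73.6%, 26.4% and 10.3% (normal), or 89.3%, 73.5%, 26.5% and 10.7% (t, 38 df).

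In each case, state that the figures assume 20 evaluable per arm, or show a range such as 16 to 20.

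The cost is a few sentences and one table. The sample size need not change; only holding 89.3% at 15% on the difference would require more participants (about 78 per arm).
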